### 6.3 MEASURES TO MINIMIZE BIAS: RANDOMIZATION AND BLINDING

Matching of Clinics- Participating clinics will be matched as closely as possible based on state, size and academic vs. non-academic / community hospital to lessen site interactions with the data.

Randomization of Clinics- Within each matched pair, one clinic will be randomly assigned to the CC condition and one will be assigned to the ECHO condition. Randomization will occur by assigning a number to each clinic using a random number generator; within each matched pair, the clinic with the lower number will be assigned to CC and the other will be assigned to ECHO.

Blinding of Research Staff- The statistician will be blinded to the identities of the clinics when assigning treatment allocation during randomization. Research staff who will contact the participants to conduct the monthly TLFB will be blinded to the treatment condition. In addition, the research staff who extract the maternal and infant outcome data

### 6.4 STUDY INTERVENTION/EXPERIMENTAL MANIPULATION ADHERENCE

Our primary outcomes are percent of pregnant women who are i) successfully engaged at least one visit per month for 3 months) and ii) retained on MAT and/or non-pharmacological care (for the purposes of this protocol, these visits will be with billable opioid use treatment providers)at delivery and through 3 months postpartum . The percent will be determined via annual baseline assessments of women who would be eligible according to an estimation of the number of women in the practice who have urine tests positive for opioids (see section D.5.d.). We define unsuccessful retention according to a modification of Wilder, et al. (2015),(98) as women who enrolled in pharmacological or behavioral treatment for opioid misuse who stopped treatment with no plan for ongoing therapy or medication for

two months (e.g. discharge, relapse and left treatment, lost to follow up with no discharge plan) during pregnancy, and the 3 months post-delivery. We add **percent engagement** as our outcome because a site may look successful in retention if they only engage a very motivated subset of eligible women in treatment yet are able to retain them. This would miss a proportion of women who may have complex illness and are more difficult to both engage and retain in treatment. We adopt a broader outcome that includes therapy rather than just initiation and continuation of MAT with input from our community partners who felt that allowing women to select either MAT and/or psychotherapy respects patient choices. We include **percent retained** because engagement is not sufficient to consider a treatment as successful. Exploratory analyses will compare the **number** of women engaged and retained in treatment. We include visits with the care manager as indicative of receiving behavioral therapy in the CC condition only if there is a specific focus on addiction treatment (e.g. recovery counseling) since that condition by default has on-site treatment available. For analysis, we would use two intervals: in pregnancy and then after delivery. Pregnancy and postpartum are very different time intervals and it is useful to differentiate them. We would then measure overall retention during the entire study period.

## 6.5 CONCOMITANT THERAPY

**Medication assisted treatment (MAT)** is a critical component of standard care for pregnant women with an OUD (35, 36) and is recommended by the **American College of Obstetricians and Gynecologists (ACOG)**(33) and other experts.(5, 37) It enhances adherence to prenatal care (38) and increases the likelihood that the mother will continue MAT after delivery, a period of high risk among perinatal women with OUD.(39) Initially MAT included methadone but now includes buprenorphine and naltrexone (not yet indicated for use in pregnancy), which can be prescribed in primary care settings.(40)

MAT status of patients can vary: women may choose to receive buprenorphine, they may receive methadone from another provider, or they may choose to receive no MAT. We would also allow women to change their decisions about MAT; we would like to respect their choice and they may decide later to engage in MAT. We will also include women who are on methadone since they may prefer to switch to buprenorphine or no MAT.

**Outside behavioral therapy-** Patients can be receiving behavioral therapy at the onset of the study or choose to begin therapy while on the study. Concomitant therapy will be recorded in the eCRFs.

### 6.5.1 RESCUE THERAPY

All practices will have a rescue protocol. This includes guidance on substance use and on suicidal plan endorsement.

#### Rescue Protocol for Substance Use

- 1) Consider increasing buprenorphine dose beyond 24 mg per day for the following reason:
  - a. Temporary elevation during third trimester to address physiologic changes in metabolism, if patient has been on 24mg per day prior to pregnancy and shows signs of withdrawal in the third trimester.

- 2) If 3 consecutive urines are positive for illicit opioids (or at least one urine positive for illicit opioids and one or more missed appointments at which additional urines would have been collected), and buprenorphine is maximized, consider transfer to a structured treatment program
  - a. Structured treatment programs can include:
    - i. methadone program or any outpatient opioid treatment program with methadone or buprenorphine along with multidisciplinary services and more supervision of medication prescriptions
    - ii. inpatient substance use treatment
    - iii. intensive outpatient treatment
  - b. Alternatively, consider increasing adjuvant treatments such as groups, counseling, Peer Support, or Recovery Coaches.
- 3) Consider a transfer of care to methadone if there is definitive evidence of diversion -for example as evidenced by 3 consecutive urine drug tests negative for buprenorphine

#### Rescue Protocol for Suicidal Ideation

- 1) If a participant endorses greater than "0" on the Edinburgh Postnatal Depression Rating Scale question # 10, the tablet will be programmed to have a hard stop. The participant will be instructed to show the scale to their nurse or doctor so that sites can employ their usual procedures to further assess suicide plans or intent and manage the patient (eg. assessment by a behavioral health care provider or referral to the emergency department)
- 2) Study personnel will work with sites that do not have a pre-existing suicide protocol to develop such a plan

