3. Participant will enter the study at different point of pregnancy. Therefore, it is likely that participants will complete varying numbers of visits between screening and the 26-week visit, and the 34-week visit and birth. This is expected and is not considered a protocol deviation. Visit 1 will follow immediately after the consenting process
4. The Time Line Follow Back will be conducted monthly during the length of the study. The number of TLFB assessments will vary depending on when the patient enters the study and when they give birth.
5. All participating centers will perform a drugs screen such as the NIDA Quick Screen or equivalent validated instrument as standard of care. If it is positive the DSM-5 OUD checklist will be completed to determine study eligibility.
6. The DSM-5 OUD Checklist will be administered to any patients who have a positive NIDA Quick Screen as part of the standard of care.
7. Birth outcomes include: low birth weight, resuscitation at delivery, fetal demise, preterm birth, duration of hospitalization.
8. The Substance Abuse Attitude Scale, the Physicians Worklife Survey and the Qualitative Interviews will be completed by physicians And done prior to the first participant being enrolled at the site and after the last participant is enrolled at the site.

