Results will be entered anonymously into a REDCAP@yale database and assigned a random subject number. Research assistants will have no contact with the patients themselves and no identifying information will be collected. Results of the urine collections will be used to determine the prevalence of substance use at each study practice. This procedure will be repeated annually during the study to ensure the accuracy of the estimate.

Recruitment of patient participants will be facilitated by universal screening by practice sites and referral to the study if appropriate. Screening for opioid misuse will occur at prenatal visits as recommended by the American College of Obstetricians and Gynecologists. Clinicians will follow up on affirmative answers and discuss study participation with them. A designated staff person (DSP) will hand potentially eligible women a tablet that includes screening questions and a patient consent document. After reviewing the consent form, and having any questions answered and signing the consent form, study participants will then complete a baseline assessment that includes demographic information and questions about pregnancy dates and a checklist that would indicate an opioid use disorder (OUD) (via a tablet computer). After completion of these questions, the tablet and DSP will determine whether the woman remains eligible for participation and will be enrolled. The participant will be assigned a study identification number. She will then complete additional questions that are part of the baseline assessment for Visit 1 (see Table 1).

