Potentially eligible women will also be given the option of having a researcher contact them by phone and reviewing the consent via phone or Yale Zoom if that is their preference. In this scenario, women will provide verbal consent to the DSP at the practice site if they are interested in being contacted by study staff, and the obstetrical provider will provide her name and contact information to research staff. Referred women will be contacted by phone or by a research assistant who will explain the entire protocol and all of its requirements at length. Additionally, women are encouraged to ask questions about any confusing points. Subjects are told that they may withdraw from the project at any time, without prejudice, and without any adverse effect on their medical care at their prenatal clinic. Women who express interest in study participation will be emailed or texted a link of the study consent form using REDCap@yale. Participants will be provided with time to review the content and the researcher will then review the eConsent form, and answer any remaining questions. Once the participant has signed and submitted the eConsent form the research assistant will receive a REDCap notification of its submission and will review the form to confirm it is filled out correctly. The research assistant will then open the corresponding 'Person Obtaining Consent' form as a survey and electronically sign it. Screening and baseline assessments as described above will then be emailed or texted to the participant.

After enrollment, a urine drug screen (UDS) will be obtained at each prenatal visit (the urine will be collected as part of the regular prenatal visit and tested for the presence of illicit and licit opiate drugs). Study sites will be asked to report results of UDS by completing a form that is entered into REDCap. Participants will also be contacted monthly by a Yale research assistant (who is blind to condition) to complete a **Time Line Follow-Back (TLFB)** and the **Treatment Utilization Form** that includes questions about the quantity and frequency of all substances used and treatment received. Study participants will complete additional self-report questionnaires at the following assessment points: enrollment, 26 weeks

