and 36 weeks (+/- 4 weeks), and at 3M post-partum. Data will be collected using a tablet provided by the DSP. In addition, maternal/infant medical record data will be extracted by the DSP and provided to the Yale and UMass data collection teams. These data will include maternal, fetal and neonatal outcomes.

In addition to the above recruitment strategies, we will also ask women who participate in the study if they know any other women who might be interested in participating. We will explain to the participant that if they know any other pregnant women who may have an opioid use disorder (i.e. known or suspected use of illicit opioids or known to be on MAT) that they can let the women know about the Project Smart Study and give our contact information. We will give our business cards to any women who think they might know someone who would be interested and they will need to contact us directly. Due to the sensitive nature of the study, we will not collect any contact information about the potential participant; she will need to contact us from the information on the business card and thus show her interest in the study.

Participants who recommend someone who consents and is eligible for the study will be compensated with a \$25 Amazon gift card for the referral.

A subset of patient participants in the trial will be given the opportunity to participate in a separate qualitative interview. These interviews will collect data on patient level of satisfaction with MAT experiences at the clinics.

The experiences of physicians involved in the project will also be assessed. At least one provider from each practice (minimum of 12) will also be invited to participate in qualitative interviews to assess their perceptions of the implementation of MAT within their practice including barriers and facilitators to implementation. All providers who participated will be asked to complete brief forms asking about workload and clinical support.

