## 6 STUDY INTERVENTION(S) OR EXPERIMENTAL MANIPULATION(S)

### 6.1 STUDY INTERVENTION(S) OR EXPERIMENTAL MANIPULATION(S) ADMINISTRATION

#### 6.1.1 STUDY INTERVENTION OR EXPERIMENTAL MANIPULATION DESCRIPTION

The sites randomized to CC will have 4-6 on-site support visits at the outset of the study. These visits will occur during the first 3 months of the project. During these visits, study staff will again review buprenorphine induction procedures (heretofore referred to as “initiation” rather than “induction”) and dosing of buprenorphine as well as therapeutic behavioral treatments. We will provide the center with forms and educational materials to help dosing during initiation procedures. At the same time, we will set up visits for the CM to meet with a recovery coach trainer provided by our community partner, CCAR. We will review data collection materials and methods.

The CC team includes the nursing CM and obstetrical provider. The CM responsibilities include: 1) screening patients for an OUD; 2) entering CC participants into the patient registry; 3) providing education to participants about OUD (and psychiatric disorders such as depression if needed); 4) assistance in initiation procedures for patients who would like to receive buprenorphine; 5) informing the obstetrical provider of a positive UDS and need to consider an increase in buprenorphine; if the patient is on methadone, the outside treatment program obtains a UDS and will make appropriate adjustments but the CM can provide support and will collect UDS as project data; 6) if the patient is not receiving MAT, a discussion about starting MAT or psychological treatment; 7) following a safety transfer protocol, a manual SOP provided to the sites by the Yale research team at the study start-up meeting; if the patient has 3 consecutive urines that are positive for illicit substances and the dose of buprenorphine is maximized (24 mgs/day), or if there is definitive evidence of diversion, or the participant is receiving any form of MAT and has dangerous level of cocaine, opioid or methamphetamine use), or is suicidal; 8) recovery coaching. For research purposes, the CM will confirm informed consent, collect and enter results of the UDS into a database. At enrollment and at 26 and 36 weeks’ gestation and 3 months postpartum she will ask participants to complete an assessment battery of self-reported measures.

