## 8 STUDY ASSESSMENTS AND PROCEDURES

### 8.1 ENDPOINT AND OTHER NON-SAFETY ASSESSMENTS

#### 8.1.1 SCREENING & BASELINE PROCEDURES

- Substance Misuse Screen – All patients seen at the participating clinical are asked substance misuse screening questions as part of their standard of care. Patients who answer affirmatively will be approached for consent.
- Demographics- Consented patients will have demographic data collected including information about pregnancy dates, medications and complications.
- Concomitant Therapy- Participants will be asked about any medications or other therapy they have received since their last visit. This information will be recorded in the eCRF.
- Medical History- Participants will be asked about their medical history. Medical history will also be collected through review of the patient's medical record if available.
- Pregnancy Questionnaire- The following information will be collected about the patient's current pregnancy; dates, medications and complications
- Urine Drug Screening- Urine collected at pre-natal visit will be tested for illicit drugs and licit opioids
- DSM-5 OUD Checklist- Patient's will complete the DSM-5 OUD checklist to confirm OUD.
- Contact Information- At least 3 verified locators will be collected for each participant. If available, one of these contacts will be a significant other who can provide collateral information and maintain subject involvement
- Self-Assessments Including:
  - Patient Activation Measure (PAM)
  - Post Traumatic Stress Disorder Checklist for DSM-5 (PCL-5)

- *Fagerstrom Test For Nicotine Dependence (FTND)*
- *HIV Risk Taking Behavior Scale (HRBS)*
- *Shared-Decision Making Questionnaire-9 (SDM-Q-9)*
- *Perceived efficacy in Patient-Physician Interactions Questionnaire (PEPPI)*
- *Kim Alliance Scale-Communication subscale (KAS-CM)*
- *PROMIS Emotional Short Form*
- *Satisfaction with Roles and Activities*
- *Edinburgh Postnatal Depression Scale (EPDS)*
- *Stigma Related Rejection Scale*
- *Adverse Childhood Experience Questionnaire*

---

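### For a baseline EPDS completed by emailed or texted link, section 6.5.1 states no prompt route from a non-zero item 10 to a clinician

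*Combined protocol and SAP*

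**What the plan says.** Section 4.1 (Overall Design) describes two ways in. In the clinic, a designated staff person (DSP) hands over a tablet; after consent and the eligibility questions, "She will then complete additional questions that are part of the baseline assessment for Visit 1". Alternatively, a researcher reviews the consent by phone or Zoom and the woman signs electronically. For that route the protocol adds: "Screening and baseline assessments as described above will then be emailed or texted to the participant".

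Section 8.1.1 lists the EPDS among the screening and baseline self-assessments, and the Schedule of Activities (1.3) also marks it at screening. Footnote 3 of the schedule says that "Visit 1 will follow immediately after the consenting process".

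The general collection rule comes at the end of 4.1. It begins "Study participants will complete additional self-report questionnaires at the following assessment points: enrollment, 26 weeks", adds the two later points, and then says "Data will be collected using a tablet provided by the DSP". Section 6.1.1 gives the same task to the care manager at collaborative care (CC) sites: at enrollment, at 26 and 36 weeks and "postpartum she will ask participants to complete an assessment battery of self-reported measures". Section 6.1.2 has the ECHO DSP hand over a tablet.

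Section 6.5.1 (Rescue Protocol for Suicidal Ideation) ties one step to EPDS item 10. A score above zero produces a hard stop on the tablet, and then "The participant will be instructed to show the scale to their nurse or doctor so that sites can employ their usual procedures". Its second item has study personnel help sites that lack a suicide protocol to write one.

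**The concern.** The item-10 step in 6.5.1 has two parts: a device that stops, and a clinician close at hand. Both suppose that the woman is in the clinic with the study tablet. The remote route in 4.1 removes both at baseline. If a woman at home scores above zero on item 10, the protocol does not say what the form shows her, who learns of the answer, or how soon.

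What is at stake is participant safety. Section 2.3.3 lists suicidal ideation as an example of clinical worsening that is common in this population, and 8.3.3.3 says the same of depression. The protocol treats any item-10 score above zero as reason to interrupt the assessment, and that reason does not depend on the device used.

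**Working it through.** No power, alpha or effect-size calculation bears on this, and the plan gives no figure to reproduce. The check is a comparison of sections, followed by a count.

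**1. Does the remote route include the EPDS?** Section 4.1 does not name the scale. The remote sentence refers back to the assessments already described, which include the further Visit 1 questions and not only the eligibility items. Section 8.1.1 places the EPDS in the screening and baseline set. Read together, the emailed or texted set includes it. Footnote 3 of the schedule gives timing only and says nothing about place or mode, so it adds little.

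**2. Which collection rule governs?** The tablet statements in 4.1 and 6.1.2, and the care-manager statement in 6.1.1, are general. The email-or-text sentence is specific to women who consent remotely. The ordinary reading is that the specific sentence is an exception to the general rule, although the protocol does not say so.

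**3. What does 6.5.1 provide for a link?** Nothing is stated. The hard stop is described for the tablet, and the follow-on step needs a nurse or doctor present.

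**4. Is any other provision triggered by the answer?**

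| Provision | Section | Arm | Tied to item 10? |
|---|---|---|---|
| Live phone or Zoom consent contact | 4.1 | Both | No; it precedes the assessments |
| Care manager finds staff if a participant becomes suicidal | 2.3.3 | Care manager is a CC role; 2.3.2 gives ECHO no explicit one | No |
| Research staff trained to escalate severe distress; psychiatrists on the team | 2.3.3 | Both | No; someone must first know |
| Rescue protocol at every practice | 6.5.1 | Both | Only through the tablet step |
| Safety transfer protocol | 6.1.1 | CC | No |
| Team review of scores, at least monthly | 6.1.2 | CC | Not stated that the EPDS is among the scores |
| First provider visit scheduled rapidly | 5.5 | Both | No; no time given |
| Initial phone interview | 5.5 (Incentives) | Both | No; timing not given |
| Monthly call on substance use and treatment | 8.1.3 | Both | No |
| Adverse-event question at each contact | 8.2 | Both | No; 8.3.4 treats a psychiatric condition present at screening as baseline unless it worsens |

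The one stated review that might show the answer is the CC team meeting, up to about one month later and only if the EPDS is among the scores reviewed. No counterpart is stated for ECHO.

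**5. How much of the EPDS schedule is involved?** The scheduled administrations are baseline (8.1.1), week 26 (8.1.4), week 36 (8.1.5) and 3 months post-partum (8.1.7), so 4. The remote wording covers baseline only: 1/4 = 25% of the schedule.

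That is not a ceiling for each woman. The week-26 window is plus or minus 4 weeks and closes at 26 + 4 = 30 weeks, while enrollment is open to pregnancies of less than 34 weeks (5.1). A woman who enters after 30 weeks has three administrations, so her share is 1/3, about 33%.

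The documents give neither the share of women who consent remotely nor the rate of item-10 scores above zero, so no count of women can be derived.

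**The case against.** The strongest reply is that this is one sentence in 6.5.1 that was not extended when a remote route was added, and that the remote route is not unattended. A researcher speaks with the woman by phone or Zoom, reviews the consent, is notified through REDCap when it is submitted, and countersigns. Research staff are trained to recognise and escalate severe distress. The schedule marks a Time Line Follow Back at screening and at Visit 1, and the payment schedule includes an initial phone interview, so a research contact around baseline is likely and the first one need not be a month away. This stands, and it narrows the gap. It does not close it, because the protocol does not say that anyone stays on the line during the assessments or looks at item 10.

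A second reply is that the detail may sit elsewhere. Section 6.1.1 refers to a manual operating procedure for safety transfer in CC, and 10.1.5 to procedures supplied to all sites. The hard stop may also be built into the emailed form. None of this can be checked here, so a gap in practice is not shown.

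Two stronger readings are tempting. A reader might infer that the protocol contradicts itself on how the baseline EPDS is collected. A general tablet rule followed by an unmarked exception for remote consent explains the text well enough; it needs a clarifying sentence, not a choice between irreconcilable statements. A reader might also infer that remotely enrolled women have no suicidality safeguard. The list in the working shows otherwise; what is missing is a trigger from this particular answer.

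**Conclusion.** The point holds in a limited form. Followed as written, a non-zero item 10 on a baseline EPDS completed by link has no stated prompt route to a clinician in either arm. This rests on two readings: that the emailed or texted baseline set includes the EPDS, and that no unseen procedure or form setting already carries the item-10 step over to the link.

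The scope is one administration, at baseline, among women who consented remotely. No text sends the week-26, week-36 or 3-month EPDS by link. The number of women concerned is unknown, and nothing in the documents shows that anyone was harmed or missed. No endpoint, sample-size figure or analysis is affected. Severity is minor: a cheap patient-safety improvement. Because 5.1 requires delivery by July 1, 2024, it matters for as long as anyone can still enroll remotely.

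**What to change.** In 6.5.1, for both arms, add that when the EPDS is completed by link, an item-10 score above zero:

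- sends an automatic REDCap alert to a designated existing study or site clinician as soon as the item is answered, without waiting for the rest of the form;
- carries a response time set by the investigators; and
- shows crisis contact information on the participant's screen.

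Alternatively, hold the EPDS for self-completion on the clinic tablet at the first visit, where the existing step works. In either case, say in 4.1 that the email-or-text route is an exception to the tablet rule and which instruments it covers. If an operating procedure already does this, citing it in 6.5.1 is enough.

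The cost is one or two sentences and, for the first option, a REDCap rule; 4.1 already uses REDCap notifications for submitted consents. Under the first option existing staff must cover the alert. Under the second the baseline EPDS is slightly delayed. If staff instead read the scale out by phone or Zoom, a self-report measure becomes interviewer-administered for some women. Depression on the EPDS is an exploratory outcome (sections 3 and 9.4.8), so that change of mode should be recorded.
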